7.1 Efficacy

All patients enrolled in the study are to be evaluated for disease activity as outlined in the Schedule of Assessments (Table 1). Screening/baseline tumor assessments should include CT with contrast of the chest, CT or MRI of the abdomen and pelvis, whole body bone scan (or PET, PET/CT), CT with contrast or MRI of the brain and evaluation of any superficial lesions. On-study assessments will include all known and suspected sites of disease and will be performed at 8-week intervals, based on a calendar beginning from first day of dosing, until approximately 1-year and then every 16 weeks; bone scans may be performed half as often as other radiology evaluations (i.e., every 16 weeks). The allowable windows for assessments are 4 weeks prior to first study treatment for screening/baseline assessments and ± 10 days for on-study disease assessments. All known and suspected sites of disease should be evaluated at each assessment.

CT scans should be performed with contrast agents unless contraindicated for medical reasons. If intravenous contrast is medically contraindicated, the imaging modality to be used (either CT without contrast or MRI) should be the modality which best evaluates the disease, and the choice should be determined by the Investigator in conjunction with the local radiologist. Depending on the adequacy for evaluation of disease, a combination of CT without contrast and MRI should most often be used. CT without contrast is preferred for evaluation of lesions in lung parenchyma. MRI is not adequate for evaluation of lung parenchyma but should also be performed to evaluate all other aspects of the chest. MRI of the abdomen and pelvis should substitute for CT with contrast

unless the method does not adequately depict the individual's disease, in which case CT without contrast is preferred.

For patients having effusions or ascites, cytological proof of malignancy should be obtained prior to selection of the effusion as a non-target lesion. Effusions that have not been evaluated using cytology or were found to be non-malignant should not be considered to be cancer lesions. New fluid collections identified on-study and existing non-malignant fluid collections that change in character require cytological proof of malignancy in order to be reported as a new lesion.

Disease response will be assessed in accordance with RECIST 1.1 ([Eisenhauer-2009](#)). [Appendix 4](#) provides guidance in using the response criteria and includes modifications to RECIST 1.1 to address potential temporary treatment effects such as tumor lesion cavitation or flare response. Assessments will be performed until objective disease progression is documented by the Investigator, or subsequent anti-cancer therapy is begun.

Patients experiencing tumor response (Partial Response [PR] or Complete Response [CR]) should undergo confirmatory assessment at least 4 weeks after initial documentation of response. It is acceptable to perform confirmatory assessments at the next appointed evaluation per protocol. Bone scan is required as an element of the confirmation of PR or CR if bone lesions were identified at the baseline assessment.

The Investigator's assessment of disease response and progression will be the basis for patient management and study expansion decision making. Potential exists for individual tumor lesions to cavitate or become otherwise difficult to evaluate for a period of time as the result of beneficial study treatment impact. For example, tumor necrosis and cavitation may result in minor increase in overall individual lesion size or unclear tumor margins prior to recovery to a smaller lesion, development of scar tissue, or complete resolution. For this reason, Investigators may delay reaching the conclusion of disease progression until subsequent on-study disease assessments are performed.

Central radiology review for disease response and progression may be implemented in this study for Cohorts 7 through 10 and would be introduced with a future amendment or an Administrative Letter. Radiographic documentation (either in digital format or original films) for independent review must be preserved and be readily available for all newly enrolled patients in these cohorts, and attempts should be made to collect and preserve such material for previously enrolled patients, for submission to a central vendor.

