The ORR using nivolumab in the population of patients with advanced/metastatic urothelial carcinoma who experienced disease progression on or after treatment with a checkpoint inhibitor is assumed to be 5% (p_0); thus, this rate is considered uninteresting. The target ORR using sitravatinib in combination with nivolumab in this study population is 30% (p_1). Stage 1 of enrollment will

include a minimum of 9 evaluable patients in each cohort. Patients included in the evaluable population will have at least one on-study disease assessment prior to discontinuation; patients who discontinue treatment due to adverse events or withdrawal of consent prior to the first on-study disease assessment will not be included in the evaluable population. With exactly 9 evaluable patients at Stage 1, if at least 1 patient has an Objective Response, 8 additional evaluable patients will be enrolled in the treatment cohort, for a total sample size of 17 evaluable patients. If at least 3 Objective Responses are observed in a treatment cohort, further investigation may be warranted. If the true ORR is 5% (null hypothesis), the probability of early termination during the study is 0.63; the Type 1 error is equal to 0.0466 and the power is equal to 0.9045.

The exact stopping rules for each cohort will be calculated based on the Predictive Probability Design, once the exact number of patients evaluable at Stage 1 is known. The aim is to include a minimum of 9 evaluable patients at Stage 1. If Stage 2 results in a cohort are of high interest for efficacy (in terms of examining the risk benefit ratio and not only in terms of ORR), enrollment may be expanded to as many as 40 patients total in that cohort to narrow the 95% Confidence Interval (CI) around the ORR point estimate and to further characterize the durability of disease control.

Table 1: Schedule of Assessments: Cohorts 1 through 8

The Schedule of Assessments provides an overview of the protocol visits and procedures. Refer to Sections 6 and 7 for detailed information on each assessment. Additional, unplanned assessments should be performed as clinically indicated, including for the purpose of fully evaluating adverse events.

Assessments	Screen/ Baseline	Cycles 1, 2, and 3		≥Cycle 4		End of Treatment		
	Within 28 days	Day 1 (± 2 days for Cycles 2 & 3)	Day 15 (± 2 days)	Day 1 (± 2 days)	Day 15 (± 2 days)	End of Treatment/ Withdrawal ¹⁴	Post Treatment Follow Up	

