- ECGs should be taken in triplicate, each reading approximately 2 minutes apart. On Cycle 1 Day 1 only, two sets of triplicate ECGs should be done within 1 hour prior to dosing (e.g., at 30-minute intervals prior to dosing) to firmly establish the baseline for the patient. One set of triplicate ECGs is required at all other timepoints. In general, ECGs should be performed prior to the respective PK blood collection. Examples of the schedule are presented below:
 - Example for Cycle 1 Day 1 pre-dose ECGs/PK: ~-1.0 hr (Triplicate ECGs); ~-30 mins (Triplicate ECGs); ~-15 mins (Vitals/PK)
 - Example for all other pre-dose ECG/PK assessments: ~-30 mins (Triplicate ECGs); ~-15 mins (Vitals/PK)
- Timepoints changed in Version 3.0 of protocol to 7 hours (5-9 hours). In preceding versions, these timepoints were 4 hours (2-6 hours).

Table 3: Schedule of Assessments: Cohorts 9 and 10

The Schedule of Assessments provides an overview of the protocol visits and procedures. Refer to Sections 6 and 7 for detailed information on each assessment. Additional, unplanned assessments should be performed as clinically indicated, including for the purpose of fully evaluating adverse events.

Assessments	Screen/ Baseline	Cycles 1, 2, and 3			≥Cycle 4		End of Treatment	
	Within 28 days	Day 1 (± 2 days for Cycles 2 & 3)	Day 8 (± 2 days)	Day 15 (± 2 days) Only Lead-in Dose Escalation of Cohort 9	Day 1 (± 2 days)	Day 8 (± 2 days)	End of Treatment/ Withdrawal ¹⁴	Post Treatment Follow Up
Study Participation Informed Consent ¹	Before study specific assessments							
Tumor Tissue Collection for PD-L1 Expression, Immune Cell Populations and Tumor Gene Alterations ²	X ²	X (Cycle 3 only) Optional ²						
Medical History, Disease History, Prior Therapy	X							
ECOG Performance Status	X							
Physical Exam ³	X						X	
Eye Exam ¹⁵	X (Within ≤ 3 months)	As clinically indicated					X	
Abbreviated Physical Exam ³		X	X	X	X	X		
Vital Signs ⁴	X	X	X	X	X	X	X	

Table 3: Schedule of Assessments: Cohorts 9 and 10 (Continued)

Assessments	Screen/ Baseline	Cycles 1, 2, and 3			≥Cycle 4		End of Treatment		
	Within 28 days	Day 1 (± 2 days for Cycles 2 & 3)	Day 8 (± 2 days)	Day 15 (± 2 days) Only Lead-in Dose Escalation of Cohort 9	Day 1 (± 2 days)	Day 8 (± 2 days)	End of Treatment/ Withdrawal ¹⁴	Post Treatment Follow Up	
Pregnancy Test ⁵	X	As clinically indicated							
Hemoglobin A1c ⁷	X								
Hematology ^{6,7}	X	X	X	X	X	X	X		
Coagulation ^{6,7}	X	As clinically indicated							

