Urinalysis ^{6,7}	X	As clinically indicated							
Serum Chemistry ^{6,7}	X	X	X	X	X	X	X		
Thyroid Function Test ^{6,7}	X	X			X		X		
Blood for Sitravatinib PK ⁸		See Table 4							
ctDNA blood sample ⁹	X	At assessment for confirmation of disease response (PR or CR)						X	
Single 12-Lead ECG ¹⁰	X	As clinically indicated						X	
Triplicate 12-Lead ECG ¹⁰		See Table 4							
Echocardiogram or MUGA	X (Within 35 days)		Cycle 3 only (± 7 days)		As clinically indicated after C3		X		
Disease Evaluation ¹¹	X	Every 9 weeks (± 10 days) for ~12 months and then every 18 weeks							
Sitravatinib Dispensing and/or Reconciliation		X			X				

Table 3: Schedule of Assessments: Cohorts 9 and 10 (Continued)

Assessments	Screen/ Baseline	Cycles 1, 2, and 3			≥Cycle 4		End of Treatment		
	Within 28 days	Day 1 (± 2 days for Cycles 2 & 3)	Day 8 (± 2 days)	Day 15 (± 2 days) Only Lead-in Dose Escalation of Cohort 9	Day 1 (± 2 days)	Day 8 (± 2 days)	End of Treatment/ Withdrawal ¹⁴	Post Treatment Follow Up	
Enfortumab and Pembrolizumab Administration		Throughout as directed in protocol (Note: pembrolizumab should be administered after sitravatinib, and enfortumab should be administered at least 30 minutes after pembrolizumab)							
Adverse Events ¹² and Concomitant Medications	SAEs only	Throughout							
Long Term Follow-up ¹³								X	

- 1 Study Participation Informed Consent: May be performed more than 28 days prior to the first dose of study treatment and must be completed prior to initiation of any study specific assessments.

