- 9 Blood samples for ctDNA analysis: Blood will be collected in two 10 mL Streck brand Cell-Free DNA Blood Collection tubes allowing shipping and stability at ambient temperatures.
- 10 12-Lead ECGs: Triplicate ECGs will accompany PK sampling as described in [Table 4](#). In addition, ECGs are to be performed as clinically indicated. Assessments will include an evaluation of heart rate, QT, and QTc intervals. RR interval should be recorded during each ECG assessment in order to calculate QTcF.
- 11 Disease Evaluations: To be performed at screening (28-day window allowed) and every 9 weeks from Cycle 1 Day 1 (\pm 10-day window for all other assessments except screening) until week 49 (~12 months) and then every 18 weeks. All on-study disease evaluations should be based on a calendar beginning from the first day of dosing. At screening/baseline, assessments are to include CT with contrast of the chest, CT or MRI of the abdomen and pelvis, as well as brain Magnetic Resonance Imaging (MRI) with and without gadolinium or CT with contrast, a whole-body bone scan (or PET or PET/CT if local standard for clinical trials) and evaluation of any superficial lesions. Subsequent disease assessments should include all sites of disease identified at baseline or suspected to have developed; bone scans may be performed half as often (every 18 weeks) as other radiology evaluations and should be performed during assessment for confirmation of disease response. More detailed guidance on exceptional circumstances is provided in the protocol. Patients who discontinued the study for reasons other than objective disease progression will continue to have disease assessments at the same frequency until patient has radiologically confirmed progression, initiates a new anticancer therapy, or death.
- 12 Adverse Events: Serious Adverse Events (SAEs) will be reported from the time of informed consent until at least 28 days after the last administration of a study treatment. Adverse events will be reported from the first day of study treatment until at least 28 days after last dose of study drug, and until resolution or stabilization of acute adverse events and/or ongoing SAEs.
- 13 Long Term Follow-up: Survival status and subsequent therapies will be collected during long term follow-up every 2 months (\pm 14 days) from the End of Treatment Visit until death or lost to follow-up. Follow-up may be performed by telephone contact or email.

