- 14 End of Treatment: Perform within 7-14 days of decision to permanently discontinue all study treatment. Assessments that have been completed in the previous 4 weeks do not need to be repeated (8 or 16 weeks for tumor assessments in accordance with schedule).
- 15 Eye exam: Patients with recent ocular complaints (within \leq 3 months of screening) must have a complete eye examination at Screening Visit performed by a qualified ophthalmologist or optometrist, including but not limited to: uncorrected, corrected and best corrected visual acuity, slit lamp, tonometry examination, and dilated fundus examination. Prior ophthalmologic exam done within 3 months of screening is acceptable provided there are no new symptoms since that exam. End of Treatment Visit slit lamp examinations are required for all patients who experience corneal adverse events during the study and must be performed \geq 28 days from last dose of enfortumab. Additional eye examinations are to be conducted as clinically indicated.

Table 4: Sitravatinib Schedule of PK, Biomarker Samples and Triplicate ECG Assessments: Cohorts 9 through 11

Collection Time and Allowable Window	Screen/ Baseline	Cycle 1 Day 1			Cycle 2 Day 1 (± 2 days)		Cycle 2, 3, 6 Day 8 only	Cycle 3 Day 1 only
		Pre-dose (-0.5-0 hour)	30 min (± 10 min)	7 hour ⁵ (5-9 hour)	Pre-dose (-0.5-0 hour)	7 hour ⁵ (5-9 hour)	Pre-dose (-0.5-0 hour)	Pre-dose (-0.5-0 hour)
PK Sample ^{1,2}	Within 28 days	X	X	X	X	X	X	
TCR Sequencing ³		X			X			
Flow Cytometry ³	X	X			X			X
Protein and Cytokine Biomarkers ³		X			X			X
Triplicate ECG ⁴		X (-1 hour)	X (-0.5 hour)	X	X	X	X	

- Scheduled vital signs and triplicate ECGs precede PK sample collection in all cases. Sitravatinib dosing and sampling should precede nivolumab infusion. Post-dose PK sample collections are not required for visits where sitravatinib dose is held but should be subsequently collected at the next visit following at least 7 days of sitravatinib intake. Alternatively, both pre-dose and post-dose PK collections are not required for visits preceded by more than 4 days or sitravatinib hold but should be subsequently collected at the next visit following at least 7 days of sitravatinib intake.

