11.6.5 Progression-Free Survival (PFS)

Progression-free survival (PFS) is defined as the time from the first dose of study drug to the date of PD or death due to any cause, whichever occurs first in the absence of documented PD. PFS (in months) will be calculated as $(\text{first event date} - \text{first dose date} + 1)/30.4375$.

PFS will be summarized descriptively using the Kaplan-Meier estimate. The median, 25th percentile, and 75th percentile of PFS and their two-sided 95% CI (Brookmeyer & Crowley, 1982) will be calculated where appropriate. In addition, minimum and maximum will also be displayed. Kaplan-Meier plots will be provided for PFS.

Analysis will be performed on the FAS.

Censoring Rules for DoR and PFS

The following censoring rules will apply to event dates for time-to-event endpoints that are based on radiographic evaluations, i.e., DOR and PFS:

- Endpoints will be censored on the date of first dose (or randomization) with duration of 1 day under the following scenarios, unless patients die within 2 consecutive tumor assessments of first dose (on or prior to week 16, i.e. Cycle 5 Day 1 plus the 10 day window, which is Study Day 122 for Cohorts 1-8 or Day 136 for Cohort 9), in which case they will be assessed as having an event on the date of death (apply to PFS only):
 - baseline disease assessment inadequate to apply RECIST1.1;
 - no disease assessments are performed during study treatment; or
 - all disease assessments performed during study treatment result in the conclusion of NE.
- Endpoints will be censored on the date of the last evaluable disease assessment prior to the start of subsequent anti-cancer therapy under the following scenarios (apply to PFS and DOR). Last evaluable assessment date is defined as the last response assessment date on or after treatment start date with a response of CR, PR, or SD.
 - PD or death occur after ≥ 2 consecutive tumor assessments (i.e., ≥ 122 days of last evaluable tumor assessment for Cohorts 1-8 or ≥ 136 days for Cohort 9) that are missed or result in the conclusion of NE;
 - patient administered subsequent anti-cancer treatment prior to documented PD or death;
 - patient lost to follow-up;
 - patient withdrawal of consent for follow-up; or
 - patients alive and without PD at the time of analysis

Date of death will be considered an event for DOR and PFS only if death occurred in the absence of receiving subsequent anti-cancer therapy, and under one of the following scenarios:

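### Section 7.1 sets 8-weekly scans for all patients but the Cohort 9 tables set 9-weekly scans; the two cannot both be followed from the third scan on, and the SAP's 136-day limit carries the wrong week and cycle anchor

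*Protocol*

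**What the plan says.** Protocol Section 7.1 begins: "All patients enrolled in the study are to be evaluated for disease activity as outlined in the Schedule of Assessments (Table 1". That sentence names no other table. On-study assessments then "will be performed at 8-week intervals, based on a calendar beginning from first day of dosing" until about one year and every 16 weeks afterwards, with a ±10-day window. The table it cites is headed "Table 1: Schedule of Assessments: Cohorts 1 through 8".

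Protocol Table 3, for Cohorts 9 and 10, gives "Every 9 weeks (± 10 days) for ~12 months and then every 18 weeks", and its footnote 11 repeats "every 9 weeks from Cycle 1 Day 1". SAP Table 3 says the same for Cohort 9. The introduction to Protocol Table 3 tells the reader: "Refer to Sections 6 and 7 for detailed information on each assessment". Footnote 14 of that table sets how recent an assessment must be to stand at End of Treatment, with the allowance "8 or 16 weeks for tumor assessments in accordance with schedule". SAP Table 3 carries the same footnote.

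SAP Section 11.6.5 describes the early-death limit for PFS as week 16, equated with Cycle 5 Day 1, plus the 10-day window, "which is Study Day 122 for Cohorts 1-8 or Day 136 for Cohort 9". The same 122 and 136 days decide whether a progression or death counts as following two or more missed or non-evaluable assessments, in which case PFS or DOR is censored at the last evaluable scan. Protocol Section 9.4.4 has a two-missed-assessment rule for PFS with no day count.

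**The concern.** Two operative passages give Cohort 9 different scan calendars, and no text says which prevails. Table 3 refers to Sections 6 and 7, Section 6.2 refers to Tables 1 and 3, and Appendix 9 refers to the main protocol. Section 7.1 is hard to read as confined to Cohorts 1 to 8, because it speaks of all enrolled patients and later discusses central review for Cohorts 7 to 10. Sections 7.2.4, 7.2.5, 7.2.6, 7.3.3 and 7.4 cite Table 3 as well as Table 1; Section 7.1, which governs the primary endpoint, does not.

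Progression is dated at the scan that finds it, so the interval affects the timing of PFS and DOR. It also determines which scans are out of window, and whether the SAP's Cohort 9 day limit matches the schedule being followed.

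**Working it through.** Days below are elapsed days from first dosing.

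**1. Reproduce the SAP limits.** Limit = 2 × interval + 10-day window.
- 8-weekly: 2 × 56 + 10 = 122, the SAP figure for Cohorts 1–8.
- 9-weekly: 2 × 63 + 10 = 136, the SAP figure for Cohort 9.

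Both are exact, and they differ by 14 days.

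**2. Check the anchor.** With 28-day cycles, Cycle 5 Day 1 is 4 × 28 = 112 days, which is week 16; 112 + 10 = 122. With Cohort 9's 21-day cycles, Cycle 5 Day 1 is 4 × 21 = 84 days, which is week 12; 84 + 10 = 94. The second 9-weekly scan is day 126, which is week 18 and Cycle 7 Day 1 (6 × 21 = 126); 126 + 10 = 136. So 136 does not follow from week 16 or from Cycle 5 Day 1.

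**3. Compare scan windows (nominal day ± 10).**

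| Scan | 8-weekly | 9-weekly | Common days |
|---|---|---|---|
| 1 | 46–66 | 53–73 | 53–66 |
| 2 | 102–122 | 116–136 | 116–122 |
| 3 | 158–178 | 179–199 | none |
| 4 | 214–234 | 242–262 | none |
| 5 | 270–290 | 305–325 | none |

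From the third scan, a scan in window under one text is out of window under the other.

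**4. Gap censoring if a Cohort 9 patient were scanned 8-weekly.** A progression or death 122 to 135 days after the last evaluable scan is an event under the 136-day limit and is censored under the 122-day limit that matches an 8-week schedule. Not every such gap means two missed scans. A scan at day 46, one missed scan, and a scan at day 178 are 178 − 46 = 132 days apart, with one scan missed. After a scan on its nominal day 56, the second later window closes at day 178, a gap of 122 days. So the two limits can classify a patient differently anywhere in this range, but which answer is right depends on where in its window the last scan fell.

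**5. Size of the timing effect.** The documents give no PFS assumption for Cohort 9. Assume exponential PFS with a true median of 2 to 8 months (30.4375 days each), scans exactly on schedule and events recorded at the next scan. With interval k and rate λ = ln 2 / median, mean lag = k / (1 − exp(−λk)) − 1/λ.
- 8-weekly: about 29 to 31 days.
- 9-weekly: about 32 to 35 days.

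The mean difference is about 4 days. A recorded median falls on a scan date, so it can move further and in either direction: a true median of 3 months is recorded as 112 against 126 days, 4 months as 168 against 126, and 2 months as 112 against 63. Over the medians tried, the shift was 14 to 49 days.

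**6. After about 12 months.** The intervals become 16 weeks (112 days) or 18 weeks (126 days).
- One interval plus the window: 112 + 10 = 122; 126 + 10 = 136.
- Two intervals plus the window: 2 × 112 + 10 = 234; 2 × 126 + 10 = 262.

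In this phase the SAP limits equal one interval plus the window. Two consecutive in-window scans can be 112 + 20 = 132 or 126 + 20 = 146 days apart with none missed, which already exceeds the limit.

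**7. Footnote 14.** On a 9-week schedule, a scan between 56 and 63 days old is on schedule but falls outside the 8-week waiver.

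**The case against.** Except for footnote 14 and the week-16 anchor, every Cohort 9-specific statement of the interval agrees on 9 weeks: the Table 3 row, its footnote 11, SAP Table 3 and the 136-day limit. Section 7.1 ties its schedule to a table limited to Cohorts 1–8, and the Table 3 sentence pointing to Section 7 is standard wording that also introduces Table 1. Section 7.1 may simply be text not updated when Cohorts 9 and 10 were added. This makes mixed practice less likely. It does not remove the contradiction, since Section 7.1 is current and covers all patients.

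Four stronger readings are tempting, and the documents do not support them.
- That Cohort 9 PFS and DOR do vary by site: nothing shows that any Cohort 9 patient was scanned 8-weekly.
- That the timing bias is as large as the calendar offset, which reaches 35 days at the fifth scan (week 45 against week 40): that offset is not a bias in PFS. Detection lag depends on interval length, and step 5 gives about 4 days on average.
- That every event at 122–135 days follows two missed scans: step 4 shows a 132-day gap with one.
- That 136 days fits the 9-week schedule throughout: step 6 shows it does not after about 12 months.

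It is also fair that actual scan dates will be visible anyway. The SAP plans tumor-assessment listings and classifies efficacy-assessment and visit-window deviations, so no new per-patient report of the interval is needed.

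**Conclusion.** The contradiction stands, and so does the mismatch between 136 days and its week-16, Cycle 5 Day 1 anchor. Both texts can be met at the first two scans but not from the third. Any effect on results is conditional on some Cohort 9 patients having been scanned 8-weekly. In that case the timing of response, PFS and DOR could shift, and some censoring decisions at 122–135 days could differ.

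The size is small. The lead-in may enroll up to 30 patients, the SAP notes that Cohort 9 Expansion and Cohort 10 will not be opened, PFS and DOR are descriptive, and dose decisions rest on Cycle 1 DLTs. Whether a response occurs is affected less than when it is recorded. The lag figures rest on the exponential assumption stated above. The post-12-month weakness of the day limits does not depend on which interval is chosen, and it applies to Cohorts 1–8 as well. This point takes no position on which scan interval is right; the passages must be reconciled.

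**What to change.** - Reconcile Protocol Section 7.1, Table 3 and footnote 14 of Table 3, and the matching SAP Table 3 footnote, to one stated Cohort 9 interval. Have Section 7.1 cite Table 3 as well as Table 1.
- In SAP Section 11.6.5, derive the Cohort 9 day limit from that interval (two intervals plus 10 days in the first year), and give a week and cycle anchor for Cohort 9 that produces it.
- In the same section, define the two-missed-scan limit separately for the phase after about 12 months, for all cohorts, and say how a gap spanning the change of interval is handled, for example by counting the scans that fell due.

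The cost is wording in an Administrative Letter or amendment, a SAP revision before database lock, and a small change to the censoring program. No new data are needed, because scan dates are already collected and listed.
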